This protocol is designed to evaluate the clinical outcomes following intramyocardial delivery of autologous UCB-MNC and is being conducted to investigate this product and its delivery procedure as a potential new therapy to strengthen the right ventricle of patients with HLHS or HLHS variants. The central hypothesis of this study is that the delivery of the autologous UCB-MNC product into the myocardium of the right ventricle of the heart at the time of Stage II surgical repair will provide a short-term improvement in cardiac function, reaching growth and developmental milestones, and quality of life, while also providing a reduction in the cumulative days of hospitalization following discharge for the Stage II surgical repair. It is also hypothesized that the autologous UCB-MNC product and its delivery procedure will ultimately provide long-term improvement in cardiac function, reaching growth and developmental milestones, reaching Stage III surgical repair pre-operative work-up, prolonging time to cardiac transplantation or death, and improving quality of life.

The safety and efficacy endpoints will be evaluated by the DSMB at least annually. This will determine the appropriateness of continued enrollment in both arms of this Phase IIb study. By demonstrating reasonable efficacy and safety of this product and its delivery procedure in this study, future definitive studies may be designed with the goal to establish a marketable regenerative therapy to treat this rare, life-threatening congenital heart disease as quickly as possible.

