Central to the hypothesis of this study is the evidence that cardiac dysfunction is a life-long complication for these individuals. Specifically, the risk of morbidity and mortality does not significantly improve even for those individuals that are able to successfully achieve Stage III Fontan circulation. Evidence indicates that 40% of patients post-Stage III either require heart transplantation, major surgical revisions, or do not survive after 12 years [4]. Furthermore, right ventricular ejection fraction (RVEF) less than 40% as measured by echocardiogram after one year post-Stage II surgery was the strongest predictor of the nearly 5% of patients that died or require cardiac transplantation within this early time period [5]. Additionally, the most common shunt used today has improved 1-yr survival rates in the Single Ventricle Trial (RV to PA conduit) yet is now associated with a long-term decline in right ventricular function and a trend towards decreased transplant-free survival likely due to ventriculotomy required in the RV at Stage I [5]. Most concerning is the reality that hypoplastic left heart syndrome patients may have the highest risk of developing right heart failure throughout the course of their clinical care for this condition [6].

Moreover, the routine imaging by echocardiography is not able to detect early ventricular dysfunction in the single right ventricle, which may be detected with the use of magnetic

resonance imaging (MRI) in these patients [7, 8]. The right ventriculotomy also leads to an aneurysmal, dyskinetic segment in the right ventricular outflow tract, seen only by MRI which adversely affects overall right ventricular systolic function in these patients [9]. Finally, cardiac transplantation is not a perfect choice to manage these patients for multiple reasons that include 4x increased morbidity and mortality rate in the high-risk single ventricle patients and only a 63% survival after 3 years for transplanted single ventricle patients [10]. Long-term mechanical support is not a practical option for these patients.

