## 2 STUDY OBJECTIVES

The purpose of this Phase IIb clinical study is to evaluate the efficacy and safety of autologous UCB-MNC intramyocardial injections into the single, morphological right ventricle of subjects with HLHS or HLHS variants requiring Stage II surgical repair. Thirty to fifty treated subjects and thirty to fifty control subjects will be accrued. Subjects accrued in the treatment arm (Arm A) of this study will be treated with a single dose following successful completion of Stage II surgical repair. Subjects accrued in the control arm (Arm B) of this study will be followed according to the same protocol requirements as the treatment arm but will not receive cell therapy. In the treatment and control arms, surrogate markers of cardiac function, growth, success in reaching Stage III surgical repair pre-operative work-up, time to cardiac transplantation or death, and cumulative days of hospitalization will be recorded and evaluated following the completion of Stage II surgery for up to four years, or until the pre-operative work-up for the Stage III surgical repair has been completed or until cardiac transplant, whichever is first. Development and quality of life as measured by questionnaires will also be monitored. Follow-up surrogate markers and the other variables noted above that are recorded for this study will be compared to baseline and by study arm. The surrogate markers and other variables are described in Section 3 of this protocol.

The objective is to evaluate the short-term (up through 3 months post-Stage II surgical repair) cardiac function, growth, and cumulative days of hospitalization following discharge for the Stage II surgical repair in the treatment and control arms, adjusting for baseline.

This evaluation will also include long-term (6 months and up to 4 years post-Stage II surgical repair or until the pre-operative work-up for the Stage III surgical repair has been completed or until cardiac transplant), cardiac function, growth, ability to reach Stage III surgical repair pre-operative work-up and time to cardiac transplantation or death in the treatment and control arms, adjusting for baseline.

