### 3.3 Long Term Endpoints

The primary long-term efficacy endpoint regarding the cell product and its delivery procedure is:

Change in right ventricular cardiac function at 12 months post-Stage II surgery compared to baseline, measured by echocardiogram.

Secondary long-term efficacy safety endpoints in their order of relevance and importance in this clinical study are:

- 1) Change in weight every 6 months post-Stage II surgery compared to baseline.
- 2) Change in heart failure medication taken every 6 months post-Stage II surgery compared to baseline.
- 3) Change in arrhythmia medication taken every 6 months post-Stage II surgery compared to baseline.

- 4) Success of subject being scheduled for Stage III surgical repair.
- 5) Time (days) until listed for cardiac transplantation, or death following the 6-month follow-up.
- 6) Change in right ventricular function at Stage III surgery pre-op work-up compared to baseline, obtained by echocardiogram, cardiac MRI, and cardiac catheterization.

Additional variables may be assessed in an exploratory manner.

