#### Lost to follow up

Follow up times for subjects who are in study at the time of analysis will be censored in time-to event analysis, as with time until listing for cardiac transplant. Since the outcome regarding time to listing includes death as part of a compound outcome, there will be no censoring for death. In case of lost to follow up before time of analysis subjects will be censored, unless the investigators feel the subject could have been indicated for transplant in which case they will be included as such in the analysis.

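### The transplant-listing-or-death endpoint has no time origin and, read literally, omits deaths before the 6-month follow-up, in conflict with other parts of the plan

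*Combined protocol and SAP*

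**What the plan says.** The protocol names death in one efficacy endpoint only, long-term secondary endpoint 5 in Section 3.3: "Time (days) until listed for cardiac transplantation, or death following the 6-month follow-up". The Clinical Study Summary has the same words, so this is not a slip in one place. The opening of Section 7 refers the analyst to Sections 3.2 and 3.3 for the endpoint definitions, so this wording governs. It does not say when the clock starts.

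Other parts of the plan set the time frame differently:

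- Section 2, first paragraph: "time to cardiac transplantation or death, and cumulative days of hospitalization will be recorded and evaluated following the completion of Stage II surgery".
- Section 2, second paragraph, on the short term: "The objective is to evaluate the short-term (up through 3 months post-Stage II surgical repair) cardiac function, growth, and cumulative days of hospitalization". It names neither death nor transplantation, and nor do the short-term endpoints in Section 3.2.
- Section 2, third paragraph: "This evaluation will also include long-term (6 months and up to 4 years post-Stage II surgical repair". Time to transplantation or death is listed under this window.
- Section 1 hypothesizes "prolonging time to cardiac transplantation or death, and improving quality of life" among the long-term benefits, with no 6-month limit.
- Section 7.3, Lost to follow up: "Since the outcome regarding time to listing includes death as part of a compound outcome, there will be no censoring for death".
- Section 7.4.4 plans Kaplan-Meier estimates and then Cox models for listing or death. It describes no landmark and no delayed entry.

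**The concern.** The cells are injected during the operation, so deaths in the following weeks and months are the ones closest in time to the intervention. If only events after the 6-month follow-up count, the arms are compared among children selected by surviving that long. That selection happens after treatment, in an open-label study without randomization. Early harm would be left out of the endpoint and could remove the frailest treated children from the later comparison. Early benefit would be left out as well. Because Section 7 does not carry the restriction, two analysts could follow different sections and report different event counts from the same data.

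**Working it through.** **1. Is a death at month 2 an event?**

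| Place | Time frame | Month-2 death |
|---|---|---|
| 3.3 item 5 and Summary, read literally | after the 6-month follow-up | not counted |
| Section 2, paragraph 1 | from the end of Stage II surgery | counted |
| Section 2, paragraph 3 | from 6 months to 4 years | outside the window |
| 7.3 and 7.4.4 | death not censored, no landmark | counted |

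A listing at month 2 is less clear still, because the time phrase in item 5 may limit death alone or both components. Section 2 also leaves a hole: the short term ends at 3 months and the long term starts at 6, so months 3 to 6 fall in neither window.

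**2. Where else could an early death count?**

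- Stage III scheduling (Section 3.3 item 4) is a yes/no outcome compared by chi-square. A child who dies early cannot reach it and can count as a failure if kept in the efficacy set. Section 7.2 limits that set to complete cell delivery (in the treated arm) and to subjects with follow-up data. It does not define follow-up data or give a rule for deaths.
- Cumulative hospital days at 1 and 3 months have no rule for deaths, and an early death can shorten the count.
- Safety: death makes an event serious (8.1.2), is a severity category (8.5) and is recorded from enrollment (6.2.1, 8.8). Adverse events are compared by severity (7.4.5).
- The death stopping rule (8.11) covers only deaths within 30 days classed as definitely related.

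**3. The plan's own figures.** Section 7.1 gives detectable effects of 0.57 (50 per arm) and 0.74 (30 per arm after 40% loss). Solving P(T > t(0.975, 2n−2)) = 0.80, with T noncentral t and noncentrality d·√(n/2), gives d = 0.566 and 0.736, so both reproduce with two-sided alpha 0.05. They concern cardiac function. The plan gives no event rate, hazard ratio or power for endpoint 5, so the rest is illustration under assumptions.

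**4. How many early deaths?** With 100 children and an assumed probability p of death before 6 months, the expected number is 100p and the chance of at least one is 1 − (1 − p)^100:

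- p = 1%: 1 death, 63%
- p = 2%: 2 deaths, 87%
- p = 5%: 5 deaths, 99%

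The only background rate is in Section 1.1: "nearly 5% of patients that died or require cardiac transplantation within this early time period". Its window is unclear, and it counts transplantation rather than listing. If it covered the first year after Stage II, 50 × 0.05 = 2.5 events per arm. With an assumed 30%, 50% or 80% of these before 6 months, 0.75, 1.25 or 2.0 events per arm would be left out, which is 1.5% to 4% of an arm of 50.

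**5. Would counting them rescue power?** Schoenfeld: power = Φ(√(D/4)·|ln HR| − 1.96), for D events, equal arms and an assumed HR of 0.5.

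- From surgery, assumed total event rate 5% to 20% of 100: D = 5 gives √1.25 × 0.693 − 1.96 = −1.185, power 12%; D = 20 gives 34%.
- After 6 months only, 25% to 75% of events assumed early: D runs from 1.25 to 15, power 6% to 27%.
- 80% power needs 66 events (Schoenfeld) or 71 (Freedman).

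**6. An example.** Suppose early deaths were 3/50 against 0/50. The literal endpoint would not register them. Counted from enrollment they would be visible, but not significant: two-sided Fisher p = 2 × C(50,3)/C(100,3) = 2 × 19,600/161,700 = 0.24.

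**The case against.** The strongest defence is that the restriction may be intended. The third paragraph of Section 2 puts this outcome in the window from 6 months, and Section 1 lists it among long-term benefits. That stands. It makes the literal reading realistic, but does not reconcile it with the first paragraph of Section 2 or with Section 7.

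Three stronger conclusions are tempting, and the documents do not support them:

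- A reader might infer that early deaths enter no efficacy endpoint. They can count as failures on Stage III scheduling, and Section 7.2 does not exclude a child who has some data after enrollment. Nor are they hidden: they are serious adverse events, compared by severity between arms. The DSMB evaluates safety at least annually and reviews the interim results.
- A reader might infer that the objective goes unanswered. Section 2 holds two time frames, and endpoint 5 agrees with one of them.
- A reader might infer that the Cox and Kaplan-Meier analyses are restricted to 6-month survivors. Sections 7.3 and 7.4.4 set no such risk set. Section 7.3 says only that death is not censored, not that every death counts whenever it occurs.

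It is also fair to say that this is the fifth of six long-term secondary endpoints, that it does not drive the sample size, and that on the Section 1.1 figure few children would be removed. The enrollment rule in Section 4.3, which screens out serious surgical complications, may make the early rate differ from published experience.

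**Conclusion.** The point holds as an unresolved conflict in the definition of the one efficacy endpoint that names death. As worded it has no time origin and literally omits deaths before 6 months, while the first paragraph of Section 2 and Sections 7.3 and 7.4.4 point to an unrestricted composite. Following the literal wording would condition a non-randomized comparison on 6-month survival.

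The likely size is a handful of events: about 1 to 5 deaths per 100 children if 1% to 5% die before 6 months. Those rates and the early-event shares are assumptions. The comparison is underpowered on either definition at the assumed hazard ratio of 0.5, so the case rests on avoiding survivor selection and having one definition, not on power. It should be corrected before analysis, but it does not threaten the primary endpoints or the sample size.

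**What to change.** In the Clinical Study Summary, Section 3.3 item 5 and Section 7.4.4, define the endpoint as time from enrollment at the Procedural Timeout (Day 0, the same origin in both arms and before any injection) to transplant listing or death from any cause, whichever is first.

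Analyse all enrolled subjects. Include treated subjects with partial delivery and subjects who die before any follow-up visit, and write this as an explicit exception to Section 7.2; otherwise the new origin would still miss some early deaths. State how Arm A subjects discontinued under Section 4.6 for a compromised product enter the analysis.

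Also:

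- align the two time frames in Section 2 and close the gap between months 3 and 6;
- add the transplant-listing date to the eCRF, since no visit list in Section 6 names it;
- state how early deaths count in Stage III scheduling and in hospital days;
- keep any post-6-month version only as a labelled supplementary landmark analysis.

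The cost is wording and one date field. Adverse events are already recorded from enrollment, and Section 4.6 already provides for survival status after withdrawal.

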## 1.1 Background

HLHS, and HLHS variants that require single ventricle palliation, are severe forms of CHD with morphological right ventricles that consist of multiple obstructions to flow through the left heart and aorta, as well as hypoplasia (underdevelopment) of the left ventricle. This combination of defects requires the affected individual to undergo surgical palliation to create a functional “single ventricle” circulation [1]. Patients are diagnosed with HLHS or HLHS variants when hypoplasia of the mitral valve, left ventricle and/or aortic valve does not allow the left ventricle to support systemic/aortic circulation. Hypoplasia is defined based upon the aortic annular dimensions, and/or left ventricular cavity dimensions and volume. Patients with HLHS have valves and chamber dimensions more than two standard deviations below the expected newborn mean value (Z scores < 2.0). Ascending aorta and aortic arch hypoplasia with coarctation often coexist with HLHS but are not defining features of the diagnosis.

For years, families were faced with making a choice between comfort care, multistage conventional surgical palliation or cardiac transplantation within the first days of life. As clinical management has improved to decrease mortality to 10-20% [2], the majority of families in the United States are electing for surgical management rather than comfort care only, with the expectation that individual patients will have ~70% chance of achieving the final Fontan circulation by the age of 5 [3]. This therapeutic option requires several palliative surgeries designed to reconstruct the patient’s circulatory system into one that can be sustained by a single right ventricle. The “single ventricle” approach requires the right ventricle to perform as the primary circulatory pump for the entire body. After initial surgery, the right ventricle is presented with the obligatory volume overloads and chronic cyanosis. These insults, combined with the need for multiple open-heart surgeries and the effects of chronically increased right ventricular myocardial afterload, often lead to progressive ventricular dysfunction and potentially life-threatening complications (i.e. protein losing enteropathy and congestive heart failure).

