#### **6.3.3 6 Month and Bi-Annual Phone Visits:**

- Changes in Concomitant Medications
- AE Assessment
- Questionnaire Completion (to be completed annually following Stage II surgery)
- Weight

At 6 and 18 months post-Stage II surgery, and every 6 months thereafter for up to 4 years (or until the pre-operative Stage III work-up or cardiac transplant), a phone follow-up with the parent(s) and/or legal guardian(s) will include the collection of the above data. In addition to specific questioning by phone follow-up, medical records should be used for documentation of changes in concomitant medications, AE assessment and subject weight.

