#### **6.3.4 Pre-Op Stage III Workup Visit:**

- Changes in Concomitant Medications
- AE Assessment
- Physical Exam (including weight)
- Vital Signs (heart rate, blood pressure, oxygen saturation)
- 12 Lead ECG
- Echo (TTE)
- Cardiac Cath (when clinically available)

When the Stage III surgery is scheduled, the date of the Stage III pre-operative work-up and the following standard of care work-up data will be collected from the subject's medical records. If data is not available, the lack of this data will not be considered a protocol deviation. The goal of collecting this data for this study is to evaluate cardiac function that is normally obtained through

standard of care pre-operative testing for the Stage III surgery, without requiring any additional research-only tests/procedures at this time point.

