#### Secondary Outcomes

Quantitative long-term outcomes will be analyzed like the primary long-term efficacy outcome of apical fractional area change. Yes/no outcome variables like “able to undergo Stage III palliative surgery” will first be analyzed by describing percent by group and the groups

compared using a chi-square test. We will analyze time-to-event outcomes, like time to listing for cardiac transplant or death, first describing naïve rates with the Kaplan-Meier method and then using Cox regression models including terms for treatment group and baseline cardiac function. If the primary analysis suggests dependency of treatment on cardiac function, we will also repeat these analyses considering cardiac function as an effect modifier by including interaction terms between group and baseline cardiac function.

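### Long-term secondary 6 (RV function at the Stage III work-up) is compared only among children who reach that work-up, which treatment may itself change, so the planned ANCOVA is a selected comparison

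*Combined protocol and SAP*

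**What the plan says.** - **Endpoint.** Section 3.3 ranks sixth and last among the long-term secondaries: "Change in right ventricular function at Stage III surgery pre-op work-up compared to baseline".
- **When it is measured.** Section 6.3.4 ties collection to scheduling ("When the Stage III surgery is scheduled, the date of the Stage III pre-operative work-up") and takes the findings from standard-of-care records. It adds: "If data is not available, the lack of this data will not be considered a protocol deviation". Under Section 6.3.3, follow-up ends at 4 years, at the work-up or at transplant, whichever is first. A child who dies, is transplanted first or is not worked up by 4 years has no value.
- **Reaching the work-up is an outcome.** The long-term hypothesis in Section 1 includes "reaching Stage III surgical repair pre-operative work-up, prolonging time to cardiac transplantation or death, and improving quality of life". Long-term secondary 4 is "Success of subject being scheduled for Stage III surgical repair".
- **Link to function.** Section 1.1 describes RVEF below 40% as the strongest predictor of early death or transplant.
- **Analysis.** Section 7.4.4: "Quantitative long-term outcomes will be analyzed like the primary long-term efficacy outcome of apical fractional area change". That means ANCOVA with terms for arm and baseline. Section 7.2 restricts efficacy analysis to children with follow-up data (and, in Arm A, full delivery). Section 7.3 allows LOCF where appropriate and otherwise leaves values missing. The attrition allowance in Section 7.1 assumes equal loss in both arms.

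**The concern.** The children with a value are selected by an event that occurs after treatment, that treatment is expected to influence, and that plausibly depends on the quantity being measured. If cells carry some weaker ventricles through to Stage III, those children enter the Arm A mean while comparable controls have no value. Adjusting for baseline function does not remove this, because the selection acts on function after Stage II.

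Secondary 6 has a place in the Section 7.3 testing sequence, so its p-value would be read as evidence about long-term RV function by arm. What it estimates is a difference between two groups of children who got to the work-up, and those groups need not be comparable. No estimand, joint analysis or sensitivity analysis is given for the others.

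**Working it through.** **The plan's own figures.** Section 7.1 gives no figure for secondary 6, only for the 3-month outcome. With two-sided alpha 0.05 and 80% power, the detectable difference is (1.960 + 0.842) × √(2/n) SD. For n = 50 this is 2.802 × 0.200 = 0.560 (0.566 with the t distribution). For n = 30 it is 2.802 × 0.258 = 0.723 (0.736 with t). The stated 0.57 and 0.74 reproduce. I use 0.57 SD as the reference effect.

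**Inputs.** From the documents: 50 per arm, 0.57 SD, and a starting value for control reach from Section 1.1 ("individual patients will have ~70% chance of achieving the final Fontan circulation by the age of 5"). That 70% covers all surgically managed patients, including losses before Stage II, so 90% is run as well. Assumed, because the documents give no value: correlation 0.5 between baseline and later function, and correlation rho between function and the propensity to reach the work-up.

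**Model.** Baseline B ~ N(0,1). Function at work-up Y = 0.5B + √0.75·e + d·A, where A is arm. Propensity L = rho·Y + √(1 − rho²)·u. A child is observed if L exceeds the cut-off that gives the stated control reach. ANCOVA of Y on A and B is then fitted in observed children only, by simulation. In the null case d = 0 and the cut-off is moved in Arm A alone.

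| Scenario | rho 1 | rho 0.7 | rho 0.5 |
|---|---|---|---|
| True 0.57, control reach 70% | 0.37 | 0.47 | 0.52 |
| True 0.57, control reach 90% | 0.47 | 0.52 | 0.54 |
| True 0, reach 70% vs 85% | -0.19 | -0.12 | -0.09 |
| True 0, reach 90% vs 95% | -0.07 | -0.05 | -0.03 |

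**Hand check without the baseline term.** The mean of Y among observed children is its arm mean plus rho × φ(c)/P(reach). For 70% reach, φ/P = 0.348/0.70 = 0.497. For 85% reach, it is 0.233/0.85 = 0.274. The null difference is rho × (0.274 − 0.497) = -0.22, -0.16 and -0.11 for the three values of rho. Baseline adjustment reduces these to the third row of the table but does not remove them.

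**Children without a value at 70% control reach.** Controls: 50 × 0.30 = 15. In Arm A with a 0.57 SD gain, reach is 79% to 86%, so about 7 to 10 of 50 are missing. Loss is unequal, contrary to the Section 7.1 allowance.

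**A second selection model.** Here a child reaches the work-up if a + g·Y + h·A + N(0,1) noise exceeds 0, where g is dependence on function, h is a separate treatment effect on reach, and a sets control reach at 70%.
- h = 0: a true 0.57 becomes 0.53, 0.47 and 0.41 for g = 0.5, 1 and 2.
- g = 1, h = 0.5: 0.57 becomes 0.40, 0.20 becomes 0.08, 0.10 becomes -0.01, and 0 becomes -0.09.
- g = 0: no bias, even with unequal reach.
- g = -1 (worse function prompts the work-up): 0.20 becomes 0.26 with h = 0.5, but 0.16 with h = 0.

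**The case against.** **Size is assumption-driven.** Enrolled children have survived Stage I and completed Stage II, and Section 4.3 keeps out those with surgical complications that threaten cardiac function. Control reach may well exceed 70%, and at 90% the distortion is small. The rho = 1 column means function alone decides who is worked up, which nothing in the documents supports. The null-case biases are also below one standard error: √(1/35 + 1/42) = 0.23 SD, before baseline adjustment. All of this stands and limits the size. It does not change what the ANCOVA estimates.

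**Part is already covered.** Reaching Stage III and time to listing or death are secondaries 4 and 5, ranked above this one, and Section 7.4.4 already reports the percentage by group for Stage III. The 12-month primary addresses long-term function at a fixed time. This also stands, so a reader who infers that the long-term objective goes unanswered goes too far. But nothing joins those results to secondary 6.

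**Apparent harm.** A reader might infer that the analysis will understate a real benefit or make cells look harmful. The documents do not support that as a prediction. When treatment acts on reach only through function, the estimate shrank but did not change sign. Reversal needed a small or null effect on function plus a separate effect on reach.

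**LOCF.** Section 7.3 could bring non-reachers back in through a 12-month echo, and the table applies only if values are left missing. The SAP does not say which applies. Carrying forward would assign a possibly pre-deterioration value to a visit that never happened, so it is not a repair.

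**Conclusion.** The point holds as a structural defect in one endpoint. Secondary 6 is observed only after an event that the protocol expects treatment to change and that plausibly depends on RV function, and the SAP analyses it as if that were not so.

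The direction most consistent with the protocol's own hypotheses is shrinkage: 0.57 SD to between 0.37 and 0.54 SD over the range run. This rests on the assumed correlations, on control reach of 70% to 90%, and on values being left missing. The bias is nil if reach is unrelated to function. It could go upward if worse function prompts the work-up and treatment also raises reach by another route.

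The consequence is limited to the last-ranked long-term secondary. It should be corrected in the SAP, but no primary result or sample size depends on it.

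**What to change.** In Sections 7.4.4 and 7.3:

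1. State that the secondary 6 ANCOVA is conditional on reaching the work-up. Label it descriptive and not evidence of a treatment effect on long-term RV function. In the same table, give the number and proportion per arm who reached the work-up, died, were transplanted or listed, were not worked up by 4 years, were lost or withdrawn, or were worked up without an echo.
2. State that LOCF is not used for a work-up that never took place.
3. Add a sensitivity analysis in all enrolled children. Rank death or transplant/listing lowest, then alive without work-up at 4 years, then measured change in FAC, and compare arms with a rank-based or proportional-odds model adjusted for baseline FAC. Treat loss to follow-up, withdrawal and work-up without data as missing, not as failure. State the order of precedence for a child who is listed and later worked up.

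The cost is SAP wording and one further analysis on data already collected. The downside is that secondary 6 no longer supports a stand-alone inferential claim. The ranked result also overlaps with secondaries 4 and 5, and it treats non-scheduling by 4 years as worse than any measured value, which is why it is proposed as a sensitivity analysis and not as a replacement endpoint.
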